**Note:**

- If lymph nodes are documented as target lesions the short axis is added into the sum of the diameters (e.g. sum of diameters is the sum of the longest diameters for non-nodal lesions and the short axis for nodal lesions). When lymph nodes decrease to non-pathological size (short axis <10mm) they should still have a measurement reported in order not to overstate progression.
- If at a given assessment time point all target lesions identified at baseline are not assessed, sum of the diameters cannot be calculated for purposes of assessing CR, PR, or SD, or for use as the nadir for future assessments. However, the sum of the diameters of the assessed lesions and the percent change from nadir should be calculated to ensure that progression has not been documented. If an assessment of PD cannot be made, the response assessment should be NE.
- All target lesions (nodal and non-nodal) should have their measurements recorded even when very small (e.g. 2 mm). If lesions are present but too small to measure, 5 mm should be recorded and should contribute to the sum of the diameters, unless it is likely that the lesion has disappeared in which case 0 mm should be reported.
- If a target lesion disappears and reappears at a subsequent time point it should continue to be measured. The response at the time when the lesion reappears will depend upon the status of the other lesions. For example, if the disease had reached a CR status then PD would be documented at the time of reappearance. However, if the response status was PR or SD, the diameter of the reappearing lesion should be added to the remaining diameters and response determined based on percent change from baseline and percent change from nadir.

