### 7.2.2. Efficacy Assessment

Disease progression and response evaluations for *intracranial* and *extracranial* disease will be determined according to the definitions established in the Response Evaluation Criteria in Solid Tumours (RECIST 1.1) [Eisenhauer, 2009]; Minor modifications will be applied to the assessment of intracranial lesions:

- **General:** target lesions should be representative of the subject's baseline tumour burden and should be selected based on their size (i.e. lesions with the longest diameter) and their suitability for accurate repeat assessment.
- **Intracranial lesions:** (the modifications to RECIST 1.1. impact the number and the minimal size of the target lesions selected at baseline) up to five lesions should be selected as target lesions; all brain lesions in excess of these five target lesions have to be regarded as non-target lesions. Measurable lesions are defined as those that can be accurately measured in at least one dimension with the longest diameter  $\geq 5$  mm when evaluated with contrast-enhanced MRI.

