#### 7.2.2.1. Assessment Guidelines

**For intracranial lesion assessments:**

- Contrast-enhanced MRI must be used throughout the study. Contrast-enhanced MRI is the only imaging modality accepted for the assessment of intracranial lesions.
- The technical specification of the MRI scanning sequences should be optimised for the evaluation of brain lesions which must be measured in the same anatomic plane by use of the same imaging examinations. Whenever possible the same scanner should be used. [Eisenhauer, 2009].
- As a modification to RECIST 1.1, target lesions as small as 5mm may be selected, however the scanning should be in accordance with RECIST 1.1: contiguous slices of maximum thickness corresponding to half the size of the lesion. [Eisenhauer, 2009] All measurements must be taken and recorded in millimetres (mm), using a ruler or callipers.
- Refer to Image Acquisition Guidelines (Brain MRI) for slice thickness requirements that should be performed in accordance with RECIST 1.1 criteria.

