### **7.3.1.1. Measurable and Non-Measurable Definitions for Extracranial Disease**

**Measurable extracranial lesion:** A non nodal lesion that can be accurately measured in at least one dimension (longest dimension) of

- $\geq 10$  mm with MRI or CT with a recommended contiguous slice thickness of 5 mm. i.e. minimum size of measurable baseline lesion should be twice the slice thickness
- $\geq 10$  mm calliper/ruler measurement or medical photography.

Additionally lymph nodes can be considered pathologically enlarged and measurable if:

- $\geq 15$ mm in the short axis when assessed by CT or MRI (slice thickness recommended to be no more than 5mm). At baseline and follow-up, only the short axis will be measured [[Eisenhauer](#), 2009].

**Non-measurable extracranial lesion:** All other lesions including lesions too small to be considered measurable (longest diameter  $< 10$  mm or pathological lymph nodes with  $\geq 10$  mm and  $< 15$  mm short axis) as well as truly non-measurable lesions, which include: ascites, pleural or pericardial effusions, inflammatory breast disease, lymphangitic involvement of the skin or lung, abdominal masses/abdominal organomegaly identified by physical exam that is not measurable by reproducible imaging techniques [[Eisenhauer](#), 2009].

**Measurable extracranial disease:** The presence of at least one measurable lesion. Palpable lesions that are not measurable by radiologic or photographic evaluations may not be utilised as the only measurable lesion.

**Non-Measurable only extracranial disease:** The presence of only non-measurable lesions.

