### **7.3.2. Response Criteria**

#### **7.3.2.1. Intracranial Response (IR) - Evaluation of Intracranial Target Lesions**

Definitions for assessment of response for *intracranial target* lesion(s) are as follows:

- Complete Response (CR): Disappearance of all target lesions.
- Partial Response (PR): At least a 30% decrease in the sum of the diameters of target lesions, taking as a reference, the baseline sum of the diameters (e.g. percent change from baseline).
- Stable Disease (SD): Neither sufficient shrinkage to qualify for PR nor sufficient increase to qualify for progressive disease.
- Progressive Disease (PD): At least a 20% increase in the sum of the diameters of target lesions, taking as a reference, the smallest sum of diameters recorded since the treatment started (e.g. percent change from nadir, where nadir is defined as the smallest sum of diameters recorded since treatment start). In addition, the sum must

have an absolute increase from nadir of 5mm.

- Not Evaluable (NE): Cannot be classified by one of the four preceding definitions.

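### A visible but unmeasurable target is recorded as 5 mm, the size of the smallest brain target allowed, so at some scans further shrinkage blocks PR or scores as PD, and no separate value is given for the intracranial sum

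*Protocol*

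**What the plan says.** Protocol section 7.2.2.1 lowers the entry size in the brain: "As a modification to RECIST 1.1, target lesions as small as 5mm may be selected". Section 7.3.1 sets the same 5 mm limit for a measurable intracranial lesion, and section 7.2.2 adds that "up to five lesions should be selected as target lesions". Outside the brain the smallest non-nodal target is 10 mm with 5 mm slices. Section 7.3.1.1 gives the principle: "minimum size of measurable baseline lesion should be twice the slice thickness".

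The rule for shrunken targets is in the note to section 7.3.2.5, on overall response, which sums brain and extracranial targets together. It has three parts:

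- Measured values come first: "All target lesions (nodal and non-nodal) should have their measurements recorded even when very small (e.g. 2 mm").
- The default follows: "If lesions are present but too small to measure, 5 mm should be recorded and should contribute to the sum of the diameters".
- The exception is: "unless it is likely that the lesion has disappeared in which case 0 mm should be reported".

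Section 7.3.2.1 sets the intracranial thresholds. PR is "At least a 30% decrease in the sum of the diameters of target lesions" relative to baseline. PD is a rise of 20% or more over the nadir, and the sum must also "have an absolute increase from nadir of 5mm". The note to 7.3.2.1 deals only with lesions that disappear and come back. SAP section 11.1 derives intracranial response from brain lesions under the protocol's criteria and adds no recording value.

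**The concern.** The protocol halved the minimum target size for the brain but left the default unchanged. For the smallest extracranial non-nodal target, 10 mm, a recorded 5 mm is a 50% decrease and so a PR. For the smallest brain target, a recorded 5 mm is no change at all.

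Because smaller measured values are recorded as measured, the recorded diameter can also go the wrong way. A lesion measured at 2 mm that then becomes too faint to measure is entered as 5 mm.

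The primary endpoint is at stake. It is a count against a threshold of 33 responders in 75, so each Cohort A subject is worth 1/75 = 1.33 percentage points. Intracranial PD also closes the window for best intracranial response (section 7.3.2.11) and ends the duration of intracranial response (SAP section 11.2).

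**Working it through.** **Inputs.** Default 5 mm, measured values kept, 0 mm if likely gone (7.3.2.5 note); minimum brain target 5 mm (7.2.2.1); up to five brain targets (7.2.2); PR at -30% from baseline, PD at +20% and +5 mm from nadir (7.3.2.1). The plan states no figure of its own to reproduce here.

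**Step 1: PR when every brain target is at the default.** For *n* targets with baseline mean *m*, the recorded sum is 5*n* and the baseline sum is *nm*. PR needs 5/*m* ≤ 0.70, so *m* ≥ 5/0.70 = 7.14 mm, whatever *n* is.

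| Baseline mean | Change at the default | Score |
|---|---|---|
| 5 mm | 0% | SD |
| 6 mm | (5-6)/6 = -16.7% | SD |
| 7 mm | (5-7)/7 = -28.6% | SD |
| 8 mm | (5-8)/8 = -37.5% | PR |
| 10 mm | (5-10)/10 = -50% | PR |

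**Step 2: where the limit does not bind.** It applies only when all targets are visible but unmeasurable at the same scan.

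- A lesion that is still measured can give PR: 5 mm at 3.5 mm or less, 6 mm at 4.2 mm or less, 7 mm at 4.9 mm or less.
- Disappearance of one target among several can be enough with the rest at 5 mm. Two of 6 mm, one gone: 12 to 5 mm, -58%. Three of 5 mm, one gone: 15 to 10 mm, -33%. Five of 6 mm, one gone: 30 to 20 mm, -33%.

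**Step 3: confirmation.** PR must be confirmed at least 4 weeks later (7.2.2 and 7.3.2.11). Take one 6 mm target. At the first scan it measures 4 mm: (4-6)/6 = -33%, PR. At the next it is smaller, visible and unmeasurable, and is recorded as 5 mm: -17%, SD. The deeper shrinkage fails to confirm the response at that scan.

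**Step 4: PD.** Suppose *n* brain targets, each measured at nadir *d*, are all later recorded at 5 mm. The absolute condition is *n*(5-*d*) ≥ 5, so *d* ≤ 5 - 5/*n*. The relative condition is 5/*d* ≥ 1.20, so *d* ≤ 4.17 mm. The absolute condition is the tighter one throughout.

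| Targets | Nadir per lesion at or below which PD is scored |
|---|---|
| 1 | none (*d* would have to be 0) |
| 2 | 2.5 mm |
| 3 | 3.3 mm |
| 4 | 3.75 mm |
| 5 | 4.0 mm |

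Example: two targets at 2 mm, sum 4 mm, are recorded as 10 mm. That is +6 mm and +150%, so both conditions are met. Two targets at 3 mm rise by only 4 mm, which is not PD.

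**The case against.** The strongest reply is that the rule does less harm than its default suggests, and most of that reply stands. A reader might infer that any subject whose brain targets average under about 7.1 mm can reach PR only if every lesion vanishes. The documents do not support this: the sentence just before the default has measured values such as 2 mm recorded, the 0 mm option covers lesions judged gone, and step 2 shows both routes to PR. Nor can shrinkage in a single target ever be scored as PD.

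Use of the default in the intracranial sum is also an inference. It is written under overall response, section 7.3.2.1 is silent, and brain MRI acquisition is partly delegated to guidelines that are not in these documents. This limits the certainty but does not remove the need for a rule. Either the 5 mm default governs the primary endpoint, or nothing does and sites may differ. Section 7.3.1 adds to the doubt by classing brain lesions under 5 mm as non-measurable, which a site could read as a reason to enter 5 mm for all of them.

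Two further limits stand. A PD scored after a response has been confirmed does not undo that response. PFS uses overall progression from the combined sum, so the +6 mm example falls below 20% once the combined nadir exceeds 6/0.20 = 30 mm.

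Finally, the PR effect makes IR too low, which is conservative for a single-arm superiority test. That is fair for the type I error, but not for the estimate or the power.

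**Conclusion.** The point holds in a limited form. A default equal to the minimum brain target size prevents PR at any scan where all brain targets are at the default and the baseline mean was under 7.14 mm. It can cost a subject the confirmation of a PR. With two or more targets at the small nadirs in step 4, it can turn shrinkage into intracranial PD. All of this assumes that the 5 mm default is carried into the intracranial sum, which the documents imply but do not state.

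A reader might want to express this as a loss of so many points of IR. That cannot be done from the documents. It would need the share of subjects whose targets are all small and the share of those that become visible but unmeasurable, and neither is given. Targets are chosen for their longest diameter and lesions up to 4 cm are eligible, so the affected group could be small. What can be said is the direction (IR too low) and the unit (1.33 points for each responder lost).

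**What to change.** - **State the value.** Section 7.3.2.1 and SAP section 11.1 should say what is recorded for a visible but unmeasurable brain target, and that a measured value under 5 mm is used as measured.
- **Cap it.** Use the lesser of 5 mm and the lesion's last recorded diameter. In step 3 the second scan is then 4 mm (-33%, PR confirmed). In the step 4 example the sum stays at 4 mm, with no PD. Lesions that return after being recorded as 0 mm should stay under the existing reappearance note.
- **Add a sensitivity analysis.** The cap does not help a 6 mm target that goes straight to unmeasurable (still 5 mm, -17%). Report IR and duration of intracranial response under a lower default, for example 2.5 mm, which is half the minimum size. This should not be the primary rule: any single target of 5 mm or more called unmeasurable would be at -50% or better, so in an open-label, investigator-assessed trial a failure to measure would itself score a PR.

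The cost is one derivation rule, one extra analysis and a small local departure from the plan's default. No new scans are needed, but intracranial response must be re-derived from diameters already recorded. The documents do not say whether the database separates a defaulted 5 mm from a measured one. If it does not, treating every post-baseline 5 mm as a default gives a bound for the sensitivity analysis.

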**7.3.2.6. Overall Response - Evaluation of Non-Target Lesions**

Overall non-target lesion response is based on all (that is, intracranial and extracranial) non-target lesions. Definitions for assessment of response for non-target lesions are as follows:

- **Complete Response (CR):** The disappearance of all non-target lesions. All lymph nodes identified as a site of disease at baseline must be non-pathological (e.g. <10 mm short axis).
- **Non-CR/Non-PD:** The persistence of 1 or more non-target lesion(s) or lymph nodes identified as a site of disease at baseline  $\geq 10$  mm short axis.
- **Progressive Disease (PD):** Unequivocal progression of existing non-target lesions.

- Not Applicable (NA): No intracranial or extracranial non-target lesions at baseline.
- Not Evaluable (NE): Cannot be classified by one of the five preceding definitions.

**Note:**

- In the presence of measurable disease, progression on the basis of solely non-target disease requires substantial worsening such that even in the presence of SD or PR in target disease, the overall tumour burden has increased sufficiently to merit discontinuation of therapy.
- In the presence of non-measurable only disease considerations should be given to whether or not the increase in overall disease burden is comparable in magnitude to the increase that would be required to declare PD for measurable disease.
- Sites of non-target lesions which are not assessed at a particular timepoint based on the assessment schedule should be excluded from the response determination (i.e., non-target response does not have to be "Not Evaluable").

**7.3.2.7. New Lesions**

New intracranial or extracranial malignancies denoting disease progression must be unequivocal. Lesions identified in follow-up in an anatomical location not scanned at baseline are considered new lesions.

Any equivocal new lesions should continue to be followed. Treatment can continue at the discretion of the investigator until the next scheduled assessment. If at the next assessment the new lesion is considered to be unequivocal, progression should be documented.

**7.3.2.8. Evaluation of Intracranial Response**

[Table 20](#) presents the intracranial response at an individual time point for all possible combinations of tumour responses in target and non-target intracranial lesions with or without the appearance of new intracranial lesions for subjects with measurable (as defined in Section [7.3.1](#)) intracranial disease at baseline.

**Table 20 Evaluation of Intracranial Response**

Target Lesions	Non-Target Lesions	New Lesions	Intracranial Response
CR	C	No	CR
CR	Non-CR/Non-PD or	No	PR
PR	Non-PD or NA or	No	PR
SD	Non-PD or NA or	No	SD
NE	Non-PD or NA or	No	NE
PD	A	Yes or No	PD
Any	P	Yes or No	PD
Any	A	Yes	PD

CR=complete response, PR = partial response, SD=stable disease, PD=progressive disease, NA= Not applicable, and NE=Not Evaluable

**Note:**

- Subjects with a global deterioration of health status requiring discontinuation of treatment without objective evidence of disease progression at that time should be classified as having "symptomatic deterioration." Objective response status is determined by evaluations of disease burden. Every effort should be made to document the objective progression even after discontinuation of treatment.
- In some circumstances, it may be difficult to distinguish residual disease from normal tissue. When the evaluation of CR depends on this determination, it is recommended that the residual lesion be investigated (fine needle aspirate/biopsy) to confirm the CR.

**7.3.2.9. Evaluation of Extracranial Response**

[Table 21](#) presents the extracranial response at an individual time point for all possible combinations of tumour responses in target and non-target extracranial lesions with or without the appearance of new extracranial lesions for subjects with measurable (as defined in Section [7.3.1](#)) extracranial disease at baseline.

**Table 21 Evaluation of Extracranial Response**

Target Lesions	Non-Target Lesions	New Lesions	Extracranial Response
CR	C	N	CR
CR	Non-CR/Non-PD or	N	PR
PR	Non-PD or NA or	N	PR
SD	Non-PD or NA or	N	SD
NE	Non-PD or NA or	N	NE
PD	A	Yes or No	PD
Any	P	Yes or No	PD
Any	A	Ye	PD

CR=complete response, PR = partial response, SD=stable disease, PD=progressive disease, NA= Not applicable, and NE=Not Evaluable

**Note:**

- Subjects with a global deterioration of health status that may require discontinuation of study treatment without objective evidence of disease progression at that time should be classified as having "symptomatic deterioration." Objective response status is determined by evaluations of disease burden. Every effort should be made to document the objective progression even if study treatment is discontinued.
- In some circumstances, it may be difficult to distinguish residual disease from normal tissue. When the evaluation of CR depends on this determination, it is recommended that the residual lesion be investigated (fine needle aspirate/biopsy) to confirm the CR.

**7.3.2.10. Evaluation of Overall Response**

[Table 22](#) presents the overall response at an individual time point for all possible

combinations of tumour responses in all intracranial and extracranial target and non-target lesions with or without the appearance of new lesions.

**Table 22 Evaluation of Overall Response**

Target Lesions	Non-Target Lesions	New Lesions	Overall Response
CR	C	No	CR
CR	Non-CR/Non-PD or	No	PR
PR	Non-PD or NA or	No	PR
SD	Non-PD or NA or	No	SD
NE	Non-PD or NA or	No	NE
PD	A	Yes or No	PD
Any	P	Yes or No	PD
Any	A	Yes	PD

CR=complete response, PR = partial response, SD=stable disease, PD=progressive disease, NA= Not applicable, and NE=Not Evaluable

**Note:**

- Subjects with a global deterioration of health status that may require discontinuation of study treatment without objective evidence of disease progression at that time should be classified as having "symptomatic deterioration". Objective response status is determined by evaluations of disease burden. Every effort should be made to document the objective progression even if study treatment is discontinued.
- In some circumstances, it may be difficult to distinguish residual disease from normal tissue. When the evaluation of CR depends on this determination, it is recommended that the residual lesion be investigated (fine needle aspirate/biopsy) to confirm the CR.

**7.3.2.11. Evaluation of Best Intracranial, Extracranial and Overall Response**

The best intracranial, extracranial, and overall response is the best response recorded from the start of the treatment until intracranial, extracranial, and overall disease progression and will be determined programmatically by Novartis based on the investigators assessment of intracranial, extracranial, and overall response at each time point.

- To be assigned a status of intracranial, extracranial, overall stable disease (SD) follow-up disease assessment must have met the SD criteria at least once after first dose of study treatment at a minimum interval of 8 weeks.
- If the minimum time for SD is not met, best response will depend on the subsequent assessments. For example if an assessment of PD follows the assessment of SD and SD does not meet the minimum time requirement the best response will be PD. Alternatively subjects lost to follow-up after an SD assessment not meeting the minimum time criteria will be considered not evaluable.

**Confirmation Criteria:**

- To be assigned a status of intracranial, extracranial, or overall PR or CR, a confirmatory disease assessment should be performed not less than 4 weeks after the

criteria for response are first met.

## 7.4. Safety

### 7.4.1. Safety Endpoints

The secondary objectives of the study include characterizing the safety of dabrafenib and trametinib combination therapy. As a consequence, clinical assessments including vital signs and physical examinations, 12-lead ECG, ECHO, chemistry and haematology laboratory values, and AEs will be monitored and evaluated.

### 7.4.2. Adverse Events

The investigator or site staff will be responsible for detecting, documenting and reporting events that meet the definition of an AE or SAE as outlined in Section [7.4.2.1](#) and Section [7.4.2.2](#) respectively.

#### 7.4.2.1. *Definition of an AE*

Any untoward medical occurrence in a patient or clinical investigation subject, temporally associated with the use of a medicinal product, whether or not considered related to the medicinal product.

**Note:** An AE can therefore be any unfavorable and unintended sign (including an abnormal laboratory finding), symptom, or disease (new or exacerbated) temporally associated with the use of a medicinal product. For marketed medicinal products, this also includes failure to produce expected benefits (i.e., lack of efficacy), abuse or misuse.

Events meeting the definition of an AE include:

- Any new primary cancer must be reported as an SAE.
- Exacerbation of a chronic or intermittent pre-existing condition including either an increase in frequency and/or intensity of the condition
- New conditions detected or diagnosed after study treatment administration even though it may have been present prior to the start of the study.
- Signs, symptoms, or the clinical sequelae of a suspected interaction.
- Signs, symptoms, or the clinical sequelae of a suspected overdose of either study treatment or a concomitant medication (overdose per se will not be reported as an AE/SAE) unless this is an intentional overdose taken with possible suicidal/self-harming intent. This should be reported regardless of sequelae.

“Lack of efficacy” or “failure of expected pharmacological action” *per se* will not be reported as an AE or SAE. However, any signs and symptoms and/or clinical sequelae resulting from lack of efficacy will be reported as an AE or SAE if they fulfill the definition of an AE or SAE.

Events that do not meet the definition of an AE include:

- Medical or surgical procedure (e.g., endoscopy, appendectomy); the condition that leads to the procedure is an AE
- Situations where an untoward medical occurrence did not occur (social and/or convenience admission to a hospital)
- Anticipated day-to-day fluctuations of pre-existing disease(s) or condition(s) present or detected at the start of the study that do not worsen
- The disease/disorder being studied, or expected progression, signs, or symptoms of the disease/disorder being studied, unless more severe than expected for the subject’s condition

